9.1. Statistical Hypotheses

The primary objective of the study is to evaluate the safety and tolerability of orally administered TERN-201. No statistical hypothesis testing will be applied.

9.2. Sample Size Determination

The sample size is based on clinical feasibility and adequate size to characterize safety in the study population, without consideration for statistical power.

Patients who are randomized but do not receive study drug for any reason may be replaced. Patients who discontinue treatment early for reasons other than safety (e.g., withdrawal of consent, lost to follow-up, patient relocated) may also be replaced. Replacement patients will receive the same treatment assignment as the patient that discontinued treatment early.

9.3. Analysis Sets

The following analysis sets are defined:

Analysis Sets	Description
Randomized	All patients who are randomized into any one of the treatment groups
PK	All randomized patients who received at least 1 dose of TERN-201 and have evaluable PK data
PD	All randomized patients who received at least 1 dose of study drug (TERN-201 or placebo) and have evaluable PD data
Safety	All patients who received at least 1 dose of study drug. Patients will be analyzed according to the intervention they actually received.
Efficacy Analysis Set	All randomized patients who received at least 1 dose of study drug. Patients will be analyzed according to the intervention they are planned to receive.
Per Protocol Analysis Set (PP)	All randomized patients who have completed the study without any major protocol deviations. The major protocol deviations will be defined in the Statistical Analysis Plan (SAP) and finalized prior to database lock (DBL). A separate completer analysis set may also be defined in the SAP.

A patient is considered to have completed the study if he/she has completed all phases of the study including the last scheduled assessment in the Follow-Up Period.

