### *Part 2*

In Part 2, if initiated, up to approximately 50 patients will receive 4 mg TERN-201 (n = 20), and/or up to 20 mg TERN-201 (n = 20), or matching placebo (n = 10) orally once daily, for 12 weeks.

In Part 2 of the study, approximately 15 randomized patients will take part in an intensive PK and PD collection after the first dose (Week 0/Day 1), at Week 6, and after the last dose of study drug (Week 12). Randomization will ensure approximately 6 patients at each TERN-201 dose level and approximately 3 patients in the placebo group are assigned to the PK/PD sub-study. Patients who are not participating in the PK/PD sub-study will have trough PK/PD sampling only.

The total duration of study participation will be approximately 22 weeks, consisting of a 6-week Screening Period, a 12-week Treatment Period and a 4-week Follow-up Period.

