**Table 4: Treatment Period Visit Windows**

Target Scheduled Visit	Target Study Day a	Analysis Window Study Day a	
		Low	High
Baseline b	1	See Section 4.7.2	
Week 2	15	2	22
Week 4	29	23	36
Week 6	43	37	50
Week 8	57	51	71
Week 12 c	85	72	92 c

a Study day will be calculated from first dose of study drug.  
b Baseline is defined in [Section 4.7.2](#).  
c LFC and cTI by MRI will have no upper limit on Week 12.

The follow up visit (Week 16) will not be windowed. As described in [Section 8.10.3.1](#), sensitivity analyses will be conducted including only Week 16 assessments which are at least 22 days from last dose.

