**Table 5: Analysis Sets**

Analysis Sets	Description
Screened	All patients who sign the informed consent form (ICF).
Randomized	All patients randomized into any one of treatment groups. Treatment assignment will be based on the randomized treatment.
Pharmacokinetic (PK)	All randomized patients who received at least 1 dose of TERN-201 and have evaluable PK data. Evaluable PK data is defined in Section 8.7 .
Pharmacodynamic (PD)	All randomized patients who received at least 1 dose of study drug (TERN-201 or placebo) and for whom at least one post baseline assessment of VAP-1/SSAO activity and methylamine is available. Treatment assignment will be based on the treatment actually received.
PK/PD Substudy	All patients who consented to the PK/PD substudy, were randomized into the PK/PD substudy, and received at least 1 dose of study drug (TERN-201 or placebo). Treatment assignment will be based on the treatment actually received.
Safety	All patients who received at least 1 dose of study drug. Treatment assignment will be based on the treatment actually received.
Efficacy	All randomized patients who received at least 1 dose of study drug. Treatment assignment will be based on the randomized treatment.
Per Protocol (PP)	All randomized patients who have completed the study without any major protocol deviations. Treatment assignment will be based on the treatment actually received.
Treatment Completer	All patients who complete 12 weeks of treatment with at least 80% compliance based on study drug accountability. Treatment assignment will be based on the randomized treatment.

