The distribution of change (percent change) values will be evaluated visually for normality assumptions. If normality assumptions are violated, first the data will be natural log transformed and the log transformed data evaluated for normality. If the data are not normally distributed, a Wilcoxon Rank Sum Test will be used to compare treatment groups. The median differences and 90% and 95% CIs of the median differences between treatment groups will be constructed using Hodges-Lehmann estimate.

Sensitivity analyses using the PP and Treatment Completer Analysis Sets will be presented if the analysis set differs from the Efficacy Analysis Set by more than 10% total.

cT1 will be categorized as low (<800 msec), elevated (800 – 900 msec), and high (>900 msec). A shift table from baseline to Week 6 and baseline to Week 12 will be presented by treatment group.

In addition, cT1 responders will be defined as any patient with a decrease of at least 80 msec. Non-responders will be defined as any patient who did not have at least an 80 msec decrease. For both endpoints, the number and percentage, with associated two-sided exact (Clopper-Pearson) 90 and 95% CIs, of patients in each category will be presented by treatment group at each post-baseline visit. A Chi-square test at each post-baseline visit will be used to compare each pairwise comparison between placebo and each active dose of TERN-201.

The number and percentage of patients who are responders on cT1 and ALT will be summarized and analyzed in the same manner as responders.

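### The Per Protocol set requires the Week 16 off-treatment visit, so a patient who misses only that visit is dropped from PP analyses of endpoints that end at Week 12

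*Protocol*

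**What the plan says.** SAP Table 5 defines the PP set as "All randomized patients who have completed the study without any major protocol deviations". Protocol 9.3 has the same definition, and directly below its table of analysis sets it says when a patient counts as having completed the study: when he or she has "completed all phases of the study including the last scheduled assessment in the Follow-Up Period".

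The last follow-up assessment is Week 16. The SAP describes participation as "consisting of a 6-week Screening Period, a 12-week Treatment Period and a 4-week Follow-up Period", and the note under SAP Table 4 says "The follow up visit (Week 16) will not be windowed".

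The SAP does not redefine completion. SAP Section 1 gives the SAP precedence over the protocol's statistical section and sends substantial differences to Section 11. The only change listed there is the addition of exploratory efficacy endpoints.

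SAP 8.10.1.1 sets out how PP is used: "Sensitivity analyses using the PP and Treatment Completer Analysis Sets will be presented if the analysis set differs" from the Efficacy set by more than 10% in total. The same conditional rule appears in 8.10.1 to 8.10.4, and by cross-reference it reaches the inflammation markers, renal markers and weight (8.10.5 to 8.10.7).

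Table 5 also has a Treatment Completer set: "All patients who complete 12 weeks of treatment with at least 80% compliance based on study drug accountability". It has no Week 16 condition.

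**The concern.** A per-protocol set is meant to show the result in patients who followed the protocol up to the measurement being analysed. Here, membership also depends on something that happens about four weeks after that measurement, off drug. For imaging, elastography and the protein biomarkers, Week 16 attendance carries no information about the endpoint or about adherence before it.

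Two things are at stake. The PP comparison loses patients whose data are complete, in arms of about 10 to 20. It is also conditioned on a post-endpoint event, and if attendance at Week 16 is related to treatment or outcome, the comparison can shift in a direction that cannot be predicted from the documents. A lesser consequence is that missed Week 16 visits count towards the 10% rule that decides whether PP results are shown, even when nothing went wrong on treatment.

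**Working it through.** **Step 1. Follow one patient through the definitions.** Take a patient who took all doses, had all Week 6 and Week 12 assessments, had no major deviation, and did not attend Week 16.

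- Protocol 9.3: study not completed, so not in PP. SAP Table 5 does not alter this.
- The exclusion comes from the completion rule. A missed Week 16 visit is not among the examples of major deviations in SAP 7.3, although that list is not exhaustive.
- PP membership is one flag per patient, so the exclusion covers every visit and every endpoint analysed on PP.
- Efficacy set (randomized and dosed): kept. Treatment Completer set: kept if compliance is at least 80%.

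**Step 2. Which PP endpoints have Week 16 data?** From the Schedule of Activities (Protocol 1.3):

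| Endpoint analysed on PP | Collected at Week 16? |
|---|---|
| cT1, MRI-PDFF | No (last at Week 12/ET) |
| Stiffness by elastography | No (last at Week 12/ET) |
| CK-18, PIIINP, TIMP-1, HA, PRO-C3, C3M | No (last at Week 12/ET) |
| hs-CRP, IL-6, ICAM-1, VCAM-1 | No (last at Week 12/ET) |
| ALT, AST, GGT | Yes |
| eGFR, UPCR, UACR | Yes |
| Weight | Yes |

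For the first four rows the Week 16 condition serves no analysis. For the last three it bears on the Week 16 analysis, but not on the on-treatment visits.

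**Step 3. Size of the loss.** The documents contain no figure to reproduce: the sample size was set without power, and no rate is given for missing Week 16 alone. The inputs are the planned arm sizes (Part 1: 20 + 10 = 30; Part 2: 20 + 20 + 10 = 50; total 80), taking all randomized patients as dosed. Rates of 2%, 5%, 10% and 15% are assumptions.

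The display threshold is the smallest k with k/N above 0.10:

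- N = 30: 3/30 = 10.0% does not exceed it; 4/30 = 13.3% does, so k = 4.
- N = 80: 8/80 = 10.0% does not exceed it; 9/80 = 11.3% does, so k = 9.

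N = 30 is a real case, because Part 2 is optional and SAP 8.3 has Part 1 locked and analysed when it completes. Expected losses are N × p. The chance of reaching the threshold through Week 16 misses alone is the binomial tail P(X ≥ k), with independent misses at a common rate:

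| Assumed rate | Expected loss, N = 30 | P(X ≥ 4) | Expected loss, N = 80 | P(X ≥ 9) |
|---|---|---|---|---|
| 2% | 0.6 | 0.003 | 1.6 | <0.001 |
| 5% | 1.5 | 0.06 | 4 | 0.02 |
| 10% | 3 | 0.35 | 8 | 0.41 |
| 15% | 4.5 | 0.68 | 12 | 0.87 |

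**Step 4. Precision.** With a common SD, the standard error of a difference is proportional to √(1/n₁ + 1/n₂).

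- Part 1, one placebo patient lost (20 v 9 instead of 20 v 10): √[(1/9 + 1/20)/(1/10 + 1/20)] = √(0.1611/0.15) = 1.036, about 4% wider.
- Part 1, two placebo patients lost: √[(1/8 + 1/20)/0.15] = √(0.175/0.15) = 1.080, about 8% wider.
- Both parts with placebo pooled to 20 (SAP 4.6), one placebo patient lost: √[(1/19 + 1/20)/(1/20 + 1/20)] = 1.013, about 1% wider.

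**The case against.** The strongest reply is that nothing important depends on this set. The main analyses of the exploratory efficacy endpoints use the Efficacy set with observed data. Safety uses the Safety set and trough VAP-1/SSAO activity uses the PD set. SAP 8.6 calls all testing nominal and exploratory. All of that stands, and it is why the point is minor.

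A second reply is that the Treatment Completer set already keeps this patient and is shown under the same rule. That is true if compliance is at least 80%. But that set does not screen for major deviations, so no set gives the deviation-free patients through Week 12.

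A third is that Week 16 is not irrelevant to PP. A reader might infer that all PP endpoints stop at Week 12. The documents do not support this: chemistry, urinalysis and weight are scheduled at Week 16, and SAP 8.10.3, 8.10.6 and 8.10.7 carry them into follow-up analyses. The objection therefore holds for the Week 16 analyses of those endpoints. It does not justify removing Week 12 MRI data.

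A fourth is that crossing the 10% threshold only adds tables. That is also right: it suppresses nothing and changes no main result.

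A reader might also fault PP for not requiring a Week 12 measurement. This has no effect, because the Week 12 ANCOVA uses observed data and a patient without the value does not enter it.

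**Conclusion.** The point holds in a limited form. As written, a patient with complete, deviation-free Week 12 data who misses only Week 16 is excluded from every PP sensitivity analysis, including those of endpoints never measured at Week 16. Patients who attend Week 16 are unaffected, so it would be wrong to infer that complete Week 12 data are discarded in general.

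The size depends on a rate the documents do not give. At 2% to 5%, missed Week 16 visits alone would rarely trigger the PP display (0.003 to 0.06 with 30 patients; at most 0.02 with 80). At 10% to 15% they often would (0.35 to 0.68, and 0.41 to 0.87). These figures assume independent misses and no other PP exclusions. The precision cost of one lost placebo patient is about 4% in Part 1 and about 1% if both parts are pooled. A reader might assume losses of 10% to 20% in every arm and a correspondingly larger cost, but nothing in the documents supports such a rate.

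No primary, secondary or main exploratory result changes. This is a free improvement.

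**What to change.** In SAP Table 5, define PP as randomized and treated patients who completed the Week 12 visit and had no major protocol deviation up to Week 12.

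Let each Week 16 analysis use the PP patients with an observed Week 16 value. This covers ALT, AST and GGT, the renal markers, weight, and the ALT change from End of Treatment (8.10.3.1). Restricting the provision to the last of these would leave out the other follow-up analyses.

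Record the change in SAP Section 11. Since the SAP takes precedence over the protocol's statistical section, no protocol amendment is needed for this.

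The cost is a sentence or two of SAP text and one changed derivation of the PP flag, with no change to data collection or conduct. It should be made before the Part 1 lock, because SAP 8.3 has Part 1 unblinded and analysed after that lock.

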9.4. Statistical Analyses

This section presents a summary of the planned statistical analyses. The SAP will provide the details and will be finalized prior to clinical database lock.

9.4.1. General Considerations

For continuous data, summary statistics will include the arithmetic mean, arithmetic standard deviation, median, minimum, maximum, and number of patients with non-missing assessments.

For log-normal data (e.g., the PK parameters: AUCs and maximum observed concentration [C_{max}]), the geometric mean and coefficient of variation (CV%) will also be presented. For categorical data, frequency counts and percentages will be presented.

9.4.2. Primary Endpoint(s)

The primary safety parameters will include TEAEs and treatment emergent clinical safety laboratory parameters.

Reported AEs will be coded using the latest version of Medical Dictionary for Regulatory Activities (MedDRA) and graded for severity according to NCI CTCAE, Version 5.0.

All TEAEs will be listed and incidence summarized by MedDRA Preferred Term and System Organ Class, as well as by maximum severity and study drug causality. Summaries of treatment emergent SAEs, TEAEs related to study drug, TEAEs resulting in study drug discontinuations, and deaths will also be produced.

Changes and percent changes from baseline of quantitative measurements will be summarized by treatment group and timepoints. Laboratory abnormalities will be graded according to NCI CTCAE Version 5.0, where applicable. Shifts in CTCAE grade from baseline will be summarized by treatment group.

Further details on the analysis of additional safety parameters will be provided in the SAP.

9.4.3. Secondary Endpoints

9.4.3.1. Pharmacokinetic Endpoints

Noncompartmental PK analysis will be performed on individual plasma and urine concentration data.

Individual plasma concentrations of TERN-201 and its metabolites, if applicable, will be listed by timepoint and summarized by treatment group. Individual and mean concentration-time profiles will be presented graphically in linear and semi-log scales.

PK parameters of TERN-201 and its metabolites (exploratory endpoint) will be listed individually and summarized with descriptive statistics, including arithmetic and geometric mean, median, standard deviation, arithmetic and geometric CV%, minimum and maximum. The C_{max} and AUC will be plotted.

9.4.3.2. Change from Baseline in Plasma VAP-1/SSAO Activity

A secondary efficacy endpoint is change from baseline in plasma VAP-1/SSAO activity with 12 weeks of treatment in patients treated with either TERN-201 or matching placebo. The change and percent change from baseline in plasma VAP-1/SSAO amine oxidase activity in each TERN-201 group will be compared with placebo separately at each post baseline visit, without controlling for any family-wise error rate (overall type I error), using MMRM (mixed model repeated measures) model with treatment group, visit, and treatment group by visit interaction as factors and baseline value as covariate.

Change and percent change from baseline plasma VAP-1/SSAO amine oxidase activity will be listed and summarized with descriptive statistics including arithmetic and geometric mean, median, standard deviation, arithmetic and geometric CV, minimum, and maximum. Exposure-response and dose-response relationships of orally administered TERN-201 will also be assessed as applicable (exploratory endpoints).

Exposure-response and dose-response analysis may be produced if Part 2 of the study is enrolled, as applicable. The change and percent change from baseline in plasma VAP-1/SSAO activity will be compared between the different TERN-201 dose groups and placebo using an analysis of covariance (ANCOVA) model with the treatment group as a factor and baseline values as a covariate. Corresponding least square mean treatment differences with 2 sided 95% confidence limits will be computed for each pairwise comparison.

Further details on the analysis models will be provided in the SAP.

9.4.4. Exploratory Endpoints

Descriptive statistics for the values, change from baseline, and percent change from baseline will be summarized by treatment group over time.

The following exploratory endpoints will be analyzed at each visit using an MMRM model similar to the model described in [Section 9.4.3.1](#). Exposure-response and dose-response analysis may be produced if Part 2 of the study is enrolled, as applicable.

- Change from baseline in cT1 by MRI
- Change from baseline in liver fat content by MRI-PDFF
- Change from baseline in stiffness by transient elastography
- Change from baseline in ALT
- Change from baseline in GGT
- Change from baseline in AST
- Change from baseline in NASH and fibrosis biomarkers
- Change from baseline in inflammatory biomarkers
- Change from baseline in eGFR, urine protein, UPCR, and UACR
- Change from baseline in plasma methylamine levels (PD marker of VAP-1/SSAO inhibition)

9.4.4.1. PD Endpoints

In addition to analyses described above, pharmacodynamic parameters (plasma VAP-1/SSAO activity and plasma methylamine levels) will be listed, summarized, and described by plotting the concentration-time curve or time-effect curve. The correlation of PK and PD parameters will also be explored.

9.5. Interim Analysis

An interim analysis will be performed after all patients in Part 1 have completed Week 6 assessments. Interim PD data will be assessed as described in [Section 9.4.4.1](#). If robust VAP-1/SSAO activity suppression is observed and available PK suggests that a lower dose may also possibly lead to robust VAP-1/SSAO activity suppression, enrollment in Part 2 with 4 mg TERN-201 may be initiated. Additionally, if safety data indicates 10 mg TERN-201 is overall safe and well-tolerated and anticipated exposures with a higher dose remain below the exposure limit (see [Section 4.3](#)), enrollment in Part 2 to assess a dose up to 20 mg TERN-201 in Part 2 may be initiated.

Additionally, an administrative interim analysis may be conducted after the completion of Part 1 of the study and will be detailed in the SAP.

10. Regulatory, Ethical, and Study Oversight Considerations

10.1. Regulatory and Ethical Considerations

This study will be conducted in accordance with the protocol and with the following:

- Consensus ethical principles derived from international guidelines including the Declaration of Helsinki and Council for International Organizations of Medical Sciences (CIOMS) International Ethical Guidelines
- Applicable International Council for Harmonisation (ICH) Good Clinical Practice (GCP) Guidelines
- Applicable laws and regulations

The protocol, protocol amendments, ICF, Investigator Brochure, and other relevant documents (e.g., advertisements) must be submitted to an IRB/IEC by the Investigator and reviewed and approved by the IRB/IEC before the study is initiated.

Any amendments to the protocol will require IRB/IEC approval before implementation of changes made to the study design, except for changes necessary to eliminate an immediate hazard to study patients.

The Investigator will be responsible for the following:

- Providing written summaries of the status of the study to the IRB/IEC annually or more frequently in accordance with the requirements, policies, and procedures established by the IRB/IEC
- Notifying the IRB/IEC of SAEs or other significant safety findings as required by IRB/IEC procedures
- Providing oversight of the conduct of the study at the site and adherence to requirements of 21 Code of Federal Regulations (CFR), ICH guidelines, the IRB/IEC, European regulation 536/2014 for clinical studies (if applicable), and all other applicable local regulations

10.1.1. Financial Disclosure

Investigators and Sub-Investigators will provide the sponsor with sufficient, accurate financial information as requested to allow the sponsor to submit complete and accurate financial certification or disclosure statements to the appropriate regulatory authorities. Investigators are responsible for providing information on financial interests during the course of the study and for 1 year after completion of the study.

10.1.2. Informed Consent Process

The Investigator or his/her representative will explain the nature of the study to the patient or his/her legally authorized representative and answer all questions regarding the study.

Patients must be informed that their participation is voluntary. Patients or their legally authorized representative will be required to sign a statement of informed consent that meets the requirements of 21 CFR 50, local regulations, ICH guidelines, Health Insurance Portability and Accountability Act (HIPAA) requirements, where applicable, and the IRB/IEC or study center.

The medical record must include a statement that written informed consent was obtained before the patient was enrolled in the study and the date the written consent was obtained. The authorized person obtaining the informed consent must also sign the ICF.

Patients must be re-consented to the most current version of the ICF(s) during their participation in the study.

A copy of the ICF(s) must be provided to the patient or the patient's legally authorized representative.

The ICF will contain a separate section that addresses the use of remaining mandatory samples for optional exploratory research for up to 15 years after the end of the study. The Investigator or authorized designee will explain to each patient the objectives of the exploratory research.

Patients will be told that they are free to refuse to participate and may withdraw their consent at any time and for any reason during the storage period. A separate signature will be required to document a patient's agreement to allow any remaining specimens to be used for exploratory research. Patients who decline to participate in this optional research will not provide this separate signature.

Written informed consent may be obtained via telephone with appropriate documentation of how the informed consent form was transmitted to the patient, (such as via email, fax, or mail) and how signature was obtained. Screening may be initiated via telephone to avoid a visit to the site if the patient is disqualified based on medical history.

